In this project, an interventional case-control study will be undertaken in four middle sized counties in the south of Sweden. Based on the case control sample also a methodological study will be realized in order to test the measurements' validity and reliability, but also a descriptive qualitative content analysis study will be accomplished. All these measurements – called triangulation – are done in order to strengthen the case-control study as a power calculation is not relevant to do due to the restricted eligible/consecutive sample as well as the restricted time schedule. Finally, based on all available data, a cost-effectiveness analysis will be undertaken with the use of a decision analytic model.

Intervention

Standard treatment

In order to replace extracted teeth after radiotherapy, the standard treatment is temporary removable dental prostheses/dentures (partial or complete). Depending on the teeth remaining, those may be completely tooth or tissue supported, or tissue and tooth supported. Temporary partial dentures are completely out of acrylic. Efforts are made to design a self-cleansing partial denture that preserves the remaining teeth and oral structures. The chewing forces are distributed evenly over the entire remaining teeth and soft tissues. Oral health related quality of life in healthy patients wearing removable dentures has previously been shown (12).

Fixed dentures

The special treatment is to within a year after completed radiotherapy replace removable dentures with tooth- or implant-supported dentures. The special treatment will begin six months after completed radiotherapy, or later depending on the severity of the side effects. Tooth- and implant-supported dentures are accepted modalities in patients with total or partial edentulous (13, 14). Patients with head and neck cancers usually follow the dental implant protocol valid for healthy individuals (15, 16). However, the fixture installation will be within a year after finished radiotherapy, when the jaws are still well supplied.

Participants

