Measurements and administration of the instruments after baseline follow the study protocol, appendix 13. The study protocol after completed radiotherapy states measurements at approximately 6 and 12 months respectively, or in severe cases after the prostheses have been used for one month. Those patients who receive the instruments by mail, will be requested to immediately respond to the instruments and return them to the research coordinator in attached envelopes (prepaid postage). A reminder is sent to the patient after one and two weeks if not responding. If necessary after another week, the patient will be contacted by telephone by the research coordinator. The patients weight will be recorded at the clinic, or self-reported by mail.

Data analysis

Parametric as well as non-parametric methods will be used in the statistical inference testing. Thus, for comparison between two groups the Student t-test and the Mann-Whitney U-test and between three groups or more Two-Way Analysis of Variance the Kruskal-Wallis One-Way Anova will be applied. For comparison of proportions between groups the Chi-square-test including standardized residual are to be used. For analysing changes over time the paired t-test or the Wilcoxon Signed Rank Test (for continuous variables) or the McNemar Test (for dichotomised variables) will be applied. For estimating relation between two continuous variables the Pearson test or Spearman

Rank Order Correlation will be used. For prediction, multiple and logistic regression are to be used and in order to adjust for confounding variables such as age logistic regressions also are to be used. The pre-chosen level of significance will be $p<0.05$ in all analyses.

Study two – qualitative approach

Interviews

A dental assistant experienced in methodological or subject experiences will interview the patients during approximately one hour twice. The dialogue will start with questions on general wellbeing, and then approaching oral health related quality of life. All the interviews will start with the question “How do you feel with regard to your health?”, followed by “Can you tell me more?”. Eventually the dental assistant asks, “How do you feel with regard to your mouth?” The interview will result in a detailed and exhaustive story from different point of views. All interviews will be recorded on minidiscs.

Data collection

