The first interview will take place approximately six months after completed radiotherapy, and the second one after approximately 12 months.

Data analysis

Qualitative content analysis described by Hsieh and Shannon (32) will be used in analysing the interviews. Each interview will be listened to in order to gain a general understanding of the content. Any content relevant to the aim will be analyzed. The text will be condensed and labelled using codes, being careful not to change the core of the meaning units based on the aims. The codes will be matched and grouped into

categories in accordance with similarities and dissimilarities. The categories will be scrutinised for underlying meanings, which will generate a number of sub-themes that reflect the content. The sub-themes will eventually be grouped under a few comprehensive themes.

Study three – validity and reliability test

Data collection

Eight patients with head and neck cancer from the Department of Maxillofacial and Oral Surgery (City of Jönköping), and eight healthy controls from the Public Dental Service Clinic (City of Jönköping) from study one will be recruited consecutively. The instruments described in study one will be completed at baseline. After 1-2 weeks, those patients (n=16) will complete the same instruments to evaluate test-retest reliability and validity.

Data analysis

Reliability

Homogeneity: Cronbach's alpha assesses internal consistency. According to Bland & Altman, Cronbach alphas of 0.70 to 0.80 are satisfactory for comparisons between groups, while an alpha of 0.90 is needed for clinical use.

Stability: Intraclass correlation coefficients (ICCs) with 95% confidence intervals are calculated per Shrout & Fleiss's ICC method based on a one-way analysis of variance (ANOVA). The concordance correlation coefficient (CCC) assesses reproducibility (temporal stability).

Validity

Content validity: Patients are asked, “Do you think the questions on aesthetics reflect the concerns you have with your mouth, your teeth and your tooth replacements (prostheses, crowns, bridges, and implants)?” They respond on a 0–10 VAS-scale with the anchors “very dissatisfied” and “very satisfied”.

Discriminative validity: Comparisons are made of OHIP-14 and GOHAI summary scores of each patient group with control groups and between patient groups. Relevant and statistically significant differences using t-tests and ANOVA are expected.

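### Study three looks for significant group differences as evidence of discriminative validity from eight patients and eight healthy controls, leaves the groups unclear, and does not say it will use the 60 planned Study one baselines

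*Protocol*

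**What the plan says.** All places are in the protocol.

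- **Study three, Data collection.** The recruits are "Eight patients with head and neck cancer from the Department of Maxillofacial and Oral Surgery (City of Jönköping), and eight healthy controls". After one to two weeks "those patients (n=16) will complete the same instruments to evaluate test-retest reliability and validity". The figure of 16 is thus attached to validity as well as to the retest.
- **Study three, Data analysis, Validity.** "Comparisons are made of OHIP-14 and GOHAI summary scores of each patient group with control groups and between patient groups". The next sentence gives the expected result: "Relevant and statistically significant differences using t-tests and ANOVA are expected". No effect size, SD or relevant difference is stated.
- **Study one, Data analysis.** "The pre-chosen level of significance will be $p<0.05$ in all analyses".
- **Design and setting.** "Based on the case control sample also a methodological study will be realized".
- **Participants.** Study one plans 30 intervention patients and 30 matched controls with the same disease. A retest in ten patients is also mentioned.
- **Study one, Data collection.** The instruments are handed out at baseline, before any treatment.
- **Study three, source of controls.** "eight healthy controls from the Public Dental Service Clinic (City of Jönköping) from study one will be recruited consecutively".

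**The concern.** Statistical significance is the result the plan looks for, and the sample explicitly tied to it is 8 against 8. In so small a comparison, significance depends as much on sample size as on whether the scale separates patients from healthy people. A scale that discriminates well could easily give p above 0.05.

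The wording also does not fit the sample. Comparisons between patient groups, and ANOVA, need more than the one patient group and one control group that Study three recruits. A reader cannot tell which groups are to be compared.

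Design and setting presents the methodological study as one of the elements meant to strengthen the case-control study, for which no power calculation was made. A discriminative check that returns an uninformative result adds little to that. Meanwhile a much larger set of patient baselines on the same instruments is planned, and the validity section does not say whether it will be used.

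**Working it through.** **Inputs from the protocol.** 8 patients and 8 healthy controls (Study three); 30 + 30 = 60 patients with planned baseline forms (Study one); significance level 0.05.

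**Assumptions.** The test is two-sided (the protocol does not say), variances are equal, and all 60 baseline forms are returned. The protocol gives no effect size, so a range of true standardised differences d is shown. There is no power figure in the plan to reproduce.

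**1. Confidence interval half-width, in pooled SD units.** Formula: t(0.975, n1+n2−2) × √(1/n1 + 1/n2).

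- 8 v 8: 2.145 × √(1/8 + 1/8) = 2.145 × 0.500 = 1.07.
- 60 v 8: 1.997 × √(1/60 + 1/8) = 1.997 × 0.376 = 0.75.
- Reduction: 1 − 0.75/1.07 = about 30%.

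The half-width is also the smallest observed difference that can reach p<0.05. With 8 v 8, an observed difference below about 1.07 SD cannot be significant.

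**2. Power.** Noncentral t with noncentrality d / √(1/n1 + 1/n2), on n1+n2−2 degrees of freedom.

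| True difference d | 8 v 8 | 60 v 8 |
|---|---|---|
| 0.5 SD | 15% | 26% |
| 0.8 SD | 32% | 55% |
| 1.0 SD | 46% | 75% |
| 1.2 SD | 61% | 88% |
| 1.5 SD | 80% | 98% |

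The difference detectable with 80% power is 1.51 SD for 8 v 8 and 1.07 SD for 60 v 8. Power with 8 v 8 passes 50% at about 1.05 SD.

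**3. Both scales significant.** By simulation (20,000 runs, 8 v 8, assumed correlation between OHIP-14 and GOHAI of 0.5 to 0.8), the chance is 6–9% at 0.5 SD, 17–22% at 0.8, 29–35% at 1.0 and 67–73% at 1.5.

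**4. Where the limit lies.** All 60 Study one patients have cancer, so they enlarge one side only. However many patients are added, the standard error cannot fall below √(1/8) = 0.354 SD, a half-width of about 1.96 × 0.354 = 0.69 SD. With 60 patients, 80% power needs 10 healthy controls at 1.0 SD, 16 at 0.8 SD and 69 at 0.5 SD.

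**5. Passages side by side.**

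- Groups: Study three recruits one patient group and one control group, but its validity text speaks of several of each. Study one has two patient groups, and Design and setting ties the methodological study to that sample.
- Retest size: ten patients under Participants, 16 people under Study three.
- Healthy controls: described as coming from Study one, which recruits only cancer patients.

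**The case against.** The strongest reply is that power hinges on an effect size the protocol does not give. The patients have head and neck tumours, dental infection and planned extractions, and the comparators are healthy, so a difference above 1 SD is possible. At 1.5 SD, 8 v 8 has 80% power. This stands. A reader might infer that the design will rarely give significance, but the documents do not support that: it depends on the assumed difference and fails above about 1.05 SD for a single scale.

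Second, the protocol states an expectation that includes relevance. It sets no pass or fail rule and makes no Study one analysis conditional on the result. Content and convergent validity are assessed too, and Swedish versions of both scales are described as already validated. This also stands. A reader might infer that valid instruments will be declared invalid, or that Study one's conclusions are put at risk; neither follows from the text.

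Third, the Study one patients may already be meant for this comparison, given Design and setting and the plural patient groups. That is possible, but the only number attached to validity is 16. The ambiguity is itself a reason to name the sample.

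Finally, adding the 60 patients does not give adequate power at 0.8 SD (55%). That is correct, and it is why the criterion should change along with the sample.

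**Conclusion.** The point holds in a limited form. On the explicit reading of n=16, the plan looks for significance from a comparison in which a null result says little unless the true difference is well above 1 SD, and part of the planned comparison has no defined groups. The power figures rest on assumed differences and the assumptions listed above. The half-widths (1.07 and 0.75 SD) need no assumed difference, but they do rest on equal variances and full return of the forms.

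Using the 60 planned baselines narrows the interval by about 30%. It is an improvement rather than a cure, because eight healthy controls set the floor. The forms are planned, not yet in hand. What is affected is the conclusion of Study three on discriminative validity.

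**What to change.** 1. State that discriminative validity compares the baseline OHIP-14 and GOHAI scores of all Study one patients (planned n=60) with the eight healthy controls.
2. Report the standardised difference with its 95% confidence interval for each scale. Judge validity on size and direction, preferably against a relevant difference stated beforehand, rather than on p<0.05.
3. Because patients from several sites would be set against controls from one Jönköping clinic, also show the comparison restricted to Jönköping patients. Their number is not stated. Intervention patients come from Jönköping and Stockholm together, so it is at most 30, and the half-width is then no better than 2.028 × √(1/30 + 1/8) = 0.81 SD.
4. Name the groups for the comparison between patient groups, or delete it together with ANOVA.
5. Reconcile the retest size (ten patients or 16 people), and correct the statement that the healthy controls come from Study one.

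The cost is wording and a few minutes of analysis, with no new participants or forms. More healthy controls would be the only way to lift the remaining limit. That is optional and would cost recruitment: 16 instead of eight would give 80% power at an assumed 0.8 SD.

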The study will take place in four middle sized counties in the south of Sweden. The intervention will include 30 patients with head and neck cancer recruited from a Department of Maxillofacial and Oral Surgery (the City of Jönköping, Jönköping County Council), and from the Department of Orofacial Medicine (the City of Stockholm, Stockholm County Council). Another 30 patients with the same disease will be matched controls recruited from another Department of Maxillofacial and Oral Surgery (the City of Linköping, County Council of Östergötland) and from five Departments of Orofacial Medicine (the Cities of Kalmar, Oskarshamn, and Västervik, Kalmar County Council; the Cities of Ljungby, and Växjö, Kronoberg County Council). If possible but not necessary, those controls may be prosthodontically rehabilitated with temporary removable dentures. The retest described in data collection study one will include ten patients diagnosed with head and neck tumor. All patients in the retest will be residents in the County of Jönköping.

The inclusion criteria are patients with head and neck tumours considered to receive radiotherapy, with or without combination of chemotherapy or surgery, good oncological prognosis at baseline ($\leq T2$). After referral from an ENT-specialist, those patients being diagnosed with dental infections and therapy planned for dental extraction(s) will be included.

The following general exclusion criteria will be applied: any communication problems; any comorbidity with poor prognosis; poor oncological prognosis (TNM-classification $>T2$) at baseline; imminent risk of recurrence; any technical, biological, or any other reasonable obstacle of treating patients with fixed dentures; and finally patients in the matched control group financing fixed oral prosthesis themselves.

Background data like sex, age, diagnosis, TNM-classification, hyposalivation, vertical jaw mobility, dysphagia, number and sites of extracted teeth, and weight will be investigated.

Study one – quantitative approach

Instruments

SF-36v2

SF-36v2 is a well established psychometric instrument with 36 items measuring eight domains of health-related quality of life: Physical function, physical role function, bodily pain, general health, vitality, social function, emotional role function, mental health. The two comprehensive indices – physical health and mental health - can be estimated for. The instrument is translated and validated into Swedish (17-19).

EQ-5D

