EQ-5D is an instrument containing five items measuring mobility, self-care, pain, role function, and anxiety/depression. There is also one item considering change of health condition and a VAS scale for general health. This instrument is also translated and validated into Swedish (20-22).

Oral health impact profile (OHIP)

OHIP-14 is an instrument consisting of 14 items (23). It was designed to provide a comprehensive measure of the dysfunction, discomfort and disability attributed to oral conditions. Validated Swedish versions of the OHIP-14 are available (24, 25).

General oral health assessment index (GOHAI)

GOHAI is a 12-item instrument originally developed for use with older adult populations, although more recently it has been used with populations of younger adults. It measures oral functional problems and also assesses the psychosocial impacts associated with oral disease (26). A Swedish version has been validated (27).

The Jaw Functional Limitation Scale (JFLS-8)

The JFLS-8 was developed for assessing limitations in mastication, jaw mobility, and verbal and emotional expression. It is recommended for clinical and research use in patient groups with varying functional limitations of the jaw. The instrument has been tested for reliability and validity (28, 29).

The Orofacial Aesthetic Scale (OAS)

The OAS consists of seven separate aesthetic aspects of the face, teeth, lips, and mouth — devoid of psychosocial aspects. These seven items create the OAS summary score. There is also an eight item, global assessment of overall impact. A Swedish version has

been validated (28, 30, 31).

Data collection

The written consent among with the instruments will be distributed to the patients at the clinic at baseline (before any treatment), appendix 4. The completed documents will be returned to a research coordinator/dental assistant at the Department of

Maxillofacial and Oral Surgery (the City of Jönköping, Jönköping County Council).

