Convergent validity: Spearman rank order correlations (ρ), assess convergent validity between (i) OHIP summary scores and self-reported health and (ii) OHIP subscale scores and subscale scores of the SF-36 and EQ-5D.

Study four – Cost-effectiveness analysis

Background

In order for a method in health- and dental care to be considered cost-effective, it has to be a decent relation between its extra costs and effects (no exact threshold value exist in Sweden). A cost-effectiveness analysis estimates the incremental cost-effectiveness ratio (ICER) of a method in comparison with the best option (33). The outcome measure can be of any (relevant) kind, but usually it is recommended to use quality-adjusted life-years (QALYs) which also is preferred by the Swedish Dental and Pharmaceutical Benefits Agency (34). QALY combines preferences for health states (QALY-weight) with the number of years of that health state.

In order to capture the full consequences of a treatment, it is often necessary to model future costs and effects into a longer time horizon. Even though these models cannot be seen as evidence, they can provide the most accurate estimate on the long-term cost-

effectiveness and they can furthermore handle uncertainty in order to provide a decision-maker with relevant information (35).

Data collection

Costs and effects of different prosthodontic rehabilitations, fixed and removable dentures, will be compared with costs and effects of radiotherapy of patients with head and neck cancer. Data on resource use will be gathered in the intervention and translated into costs, representing their best alternative use. Productivity loss of patients unable to work will be estimated using the human capital approach. The main outcome measure in the analysis will be QALY. QALY-weights are derived indirectly from the instruments EQ-5D and SF-6D, and directly from the EQ-VAS, all of which are analysed in Study one in this project. Other outcome measures that are more directly derived from oral health related quality of life will be used too in order to examine their relevance.

Data analysis

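### Convergent validity of OHIP is planned only against general health measures, leaving out GOHAI, and it is unclear whether 16 people or the planned 60 cancer patients supply the data

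*Protocol*

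**What the plan says.** The Validity part of Study three names the convergent analysis in full. Spearman correlations are to "assess convergent validity between (i) OHIP summary scores and self-reported health", and second between "OHIP subscale scores and subscale scores of the SF-36 and EQ-5D". No other comparator is listed.

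Study one, Instruments, describes SF-36v2 and EQ-5D as measures of general health. It describes OHIP-14 as a measure of dysfunction, discomfort and disability due to oral conditions. Of GOHAI it says: "It measures oral functional problems and also assesses the psychosocial impacts associated with oral disease". JFLS-8 covers jaw function and OAS covers orofacial appearance. In the Validity part, GOHAI stands beside OHIP-14 only under discriminative validity.

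On who supplies the data, Study three, Data collection, says "The instruments described in study one will be completed at baseline" and then "those patients (n=16) will complete the same instruments to evaluate test-retest reliability and validity". The 16 are eight cancer patients and eight healthy controls. Design and setting, however, bases the methodological study on the case-control sample. Participants plans that sample as 30 intervention patients and 30 matched controls with the same disease, and Study one, Data collection, gives the instruments to these patients at baseline.

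**The concern.** Convergent validity asks whether two measures of the same construct agree. A correlation of OHIP with mobility or self-care bears only indirectly on that. The closest available comparator, GOHAI, is already on the same form but is left out of this test, as are JFLS-8 and OAS.

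The sample raises two further problems if it is the 16. First, a moderate correlation would be estimated too imprecisely to interpret. Second, half the 16 are healthy. The protocol itself expects OHIP-14 and GOHAI to differ between patients and controls, and a group difference on two scales produces a correlation between them even when they are unrelated within each group.

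At stake is the psychometric support that the project wants from Study three, not the treatment comparison itself.

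**Working it through.** **The plan's own figures.** The protocol gives no expected rho and no precision target, so there is no figure to reproduce. Its counts add up: 8 + 8 = 16 and 30 + 30 = 60.

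**Inputs.** n = 16 (Study three, Data collection); n = 60 (Participants); significance level 0.05 (Study one, Data analysis), taken as two-sided. The values of rho are assumptions, shown over 0.3 to 0.8.

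**Precision.** The 95% CI for a Spearman rho is tanh(atanh(rho) ± 1.96 × SE), with SE = sqrt(1.06/(n − 3)). For rho = 0.5, atanh(0.5) = 0.549.

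- n = 16: SE = sqrt(1.06/13) = 0.286; limits tanh(0.549 ± 0.560), that is -0.01 to 0.80.
- n = 60: SE = sqrt(1.06/57) = 0.136; limits tanh(0.549 ± 0.267), that is 0.27 to 0.67.

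Over the assumed range:

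| rho | 95% CI, n = 16 | 95% CI, n = 60 |
|---|---|---|
| 0.3 | -0.25 to 0.70 | 0.04 to 0.52 |
| 0.5 | -0.01 to 0.80 | 0.27 to 0.67 |
| 0.7 | 0.30 to 0.89 | 0.54 to 0.81 |
| 0.8 | 0.49 to 0.93 | 0.68 to 0.88 |

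With the alternative SE sqrt((1 + rho²/2)/(n − 3)), rho = 0.5 gives -0.03 to 0.81 and 0.27 to 0.68, so the choice of formula does not matter here.

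**Smallest significant correlation.** This is t/sqrt(n − 2 + t²) on n − 2 degrees of freedom: 0.497 at n = 16 and 0.254 at n = 60. An observed 0.5 at n = 16 is therefore on the boundary: the t-approximation just passes it, and the interval above just fails it.

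**Power at a true rho of 0.5.** By the normal approximation, Φ(0.549/SE − 1.96) is about 49% at n = 16 and 98% at n = 60.

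**Pooling patients with healthy controls.** Take two equal groups with no correlation within either, and a shift of d standard deviations on both scales. The pooled product-moment correlation is (d²/4)/(1 + d²/4), which is 0.20, 0.36 and 0.50 for d = 1, 1.5 and 2. A simulation of 5,000 samples of 8 + 8 gave mean Spearman rho of 0.21, 0.38 and 0.54, with p < 0.05 in 13%, 33% and 63% of samples.

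The shifts are assumed, but they are not extreme for this plan. For a t-test of 8 against 8 to reach significance, the observed difference must be at least 2.145 × sqrt(1/8 + 1/8) = 1.07 SD.

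**What the design needs.** Test-retest needs two administrations and hence the retest subset. A convergent correlation needs one administration, so nothing in the design confines it to the 16.

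**The case against.** The strongest reply is that n = 16 is not clearly the convergent sample. The figure is attached to the repeat administration, the convergent paragraph gives no n, and Design and setting points to the case-control sample. This stands in part: a reader might infer that the protocol plainly limits convergent validity to 16 people, and it does not. But Study three, Data collection, does tie validity to the 16, so the sections conflict and must be reconciled.

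It can also be said that OHIP against SF-36 and EQ-5D is a useful question. The aim includes general wellbeing, and Study four takes QALY weights from EQ-5D and SF-6D. That is right, and is a reason to keep these correlations. It is not a reason to omit GOHAI. The general provision for correlations in Study one, Data analysis, would allow OHIP-14 against GOHAI, but does not make it part of the named convergent analysis.

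Three stronger readings are tempting and not supported:

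- That 16 people could not show agreement between OHIP-14 and GOHAI. If the scales are as close as described, rho may be 0.7 or more, and the interval then excludes zero even at n = 16. It remains wide.
- That the many subscale correlations would yield a calculable number of false positives. Such a count assumes that every true correlation is zero, which is implausible, and the protocol does not give the number of OHIP subscales.
- That 60 completed forms are already available. They are planned, and fewer may be returned.

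**Conclusion.** The concern holds in limited form. The protocol names general health measures as the only convergent comparators for OHIP and passes over GOHAI, which its own description makes the closest match. That self-reported health means general health is the plain reading of an undefined term. That GOHAI and OHIP-14 overlap closely is a judgement resting on the two descriptions in Study one.

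The sample for the analysis is stated inconsistently. If it is the 16, the interval at an assumed rho of 0.5 is about 0.81 wide (-0.01 to 0.80), against 0.40 with 60 (0.27 to 0.67), and pooling can create correlation where none exists within groups. If it is the full case-control sample, the precision problem largely goes and only the choice of comparator remains.

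The consequence is small. Study one says that validated Swedish versions of OHIP-14 and GOHAI exist, and no decision rule in Study one or Study four depends on this result. This is a worthwhile improvement, not a flaw that threatens the project.

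**What to change.** Amend Study three, Data collection and Validity, and align them with Design and setting:

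- Use all returned Study one baseline forms from cancer patients (planned 60) for convergent validity. Keep the 16 for test-retest.
- Make OHIP-14 against GOHAI summary scores the main convergent test, followed by JFLS-8 and OAS summary scores. State the expected sign of each and report 95% CIs.
- Keep SF-36 and EQ-5D as secondary comparators, with lower correlations expected, and say which item self-reported health refers to.
- Do not pool healthy controls with patients in any convergent correlation.

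The same edit should settle the retest sample. Participants says "The retest described in data collection study one will include ten patients diagnosed with head and neck tumor", against 16 people in Study three. Study three also takes its healthy controls from Study one, whose controls have cancer.

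The cost is a few extra correlations on forms the project already plans to collect, with no added burden on patients.
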